Programming note: A similar table will be presented for Part 2, with the column headers for each of the 3 groups

OMO-103-01
Table 14.3.1.6
Serious Adverse Events - Part 1 - (1)
Safety Set

<Cohort X>

Subject	Event Number	System Organ Class/ Preferred Term/ Reported Term	Onset Date /Time	End Date/ Time/Ongoing	Date Reported	Severity	Relationship to Study Drug
xxx	x	xxxxxxxxx/ xxxxxxxxx/ xxxxxxxxx	xxxxxxx Txx:xx	xxxxxxx Txx:xx	xxxxxxx	xxxxxxx	xxxxxxx
xxx	x	xxxxxxxxx/ xxxxxxxxx/ xxxxxxxxx	xxxxxxx Txx:xx	xxxxxxx Txx:xx	xxxxxxx	xxxxxxx	xxxxxxx
	x	xxxxxxxxx/ xxxxxxxxx/ xxxxxxxxx	xxxxxxx Txx:xx	xxxxxxx Txx:xx	xxxxxxx	xxxxxxx	xxxxxxx
xxx	x	xxxxxxxxx/ xxxxxxxxx/ xxxxxxxxx	xxxxxxx Txx:xx	xxxxxxx Txx:xx	xxxxxxx	xxxxxxx	xxxxxxx

Source Listing: 16.2.8.1; Produced: yyyy-mm-ddThh:mm - Page x of y
Duration: (Date/Time of Resolution-Date/Time of Onset) + 1 minute.
Time from Dose: (Date/Time of Onset-Date/Time of Start of Dose).
SAE = Serious Adverse Event.
MedDRA version <x.x>.

*Programming Note: This table will be repeated on a new page for each cohort (or group in part 2)
This table will be repeated for Part 2. Similar tables will be presented for Adverse Events Leading to Withdrawal - Part 1 and Part 2 (Table 14.3.1.7).*

OMO-103-01
Table 14.3.1.6
Serious Adverse Events - Part 1 - (2)
Safety Set

<Cohort X>

Subject	Event Number	System Organ Class/ Preferred Term/ Reported Term	Duration (dd:hh:mm)	Day Post Dose	Time Post Dose (xx:xx)	SAE	SAE Criteria	Action	Outcome	Comment
xxx	x	xxxxxxxxx/ xxxxxxxxx/ xxxxxxxxx	xx:xx:xx	xx	xx:xx	x	xxxxxxxxxxxxx	xxxxxx	xxxxxx	xxxxxxxxx
xxx	x	xxxxxxxxx/ xxxxxxxxx/ xxxxxxxxx	xx:xx:xx	xx	xx:xx	x	xxxxxxxxxxxxx	xxxxxx	xxxxxx	xxxxxxxxx
	x	xxxxxxxxx/ xxxxxxxxx/ xxxxxxxxx	xx:xx:xx	xx	xx:xx	x	xxxxxxxxxxxxx	xxxxxx	xxxxxx	xxxxxxxxx
xxx	x	xxxxxxxxx/ xxxxxxxxx/ xxxxxxxxx	xx:xx:xx	xx	xx:xx	x	xxxxxxxxxxxxx	xxxxxx	xxxxxx	xxxxxxxxx

Source Listing: 16.2.8.1; Produced: yyyy-mm-ddThh:mm - Page x of y
 Duration: (Date/Time of Resolution-Date/Time of Onset) + 1 minute.
 Time from Dose: (Date/Time of Onset-Date/Time of Start of Dose).
 SAE = Serious Adverse Event.
 MedDRA version <x.x>.

*Programming Note: This table will be repeated on a new page for each cohort (or group in part 2)
 This table will be repeated for Part 2. Similar tables will be presented for Adverse Events Leading to Withdrawal - Part 1 and Part 2 (Table 14.3.1.7).*

OMO-103-01
Table 14.3.2.1
Biochemistry Out of Normal Range Data - Part 1
Safety Set

Subject	Visit/ Time Point	Sample Date/Time	Sample ID	Parameter	Result	Unit	Flag	Normal Range	
								Low	High
xxx	xxxxxx	xxxxxxxxxx	xxxxx	xxxxxxx	x.xx	xxx	x	x.x	x.xx
				xxxxxxx	x.xx	xxx	x	x.x	x.xx
				xxxxxxx	x.xx	xxx	x	x.x	x.xx
				xxxxxxx	x.xx	xxx	x	x.x	x.xx
	xxxxxx	xxxxxxxxxx	xxxxx	xxxxxxx	x.xx	xxx	x	x.x	x.xx
				xxxxxxx	x.xx	xxx	x	x.x	x.xx
				xxxxxxx	x.xx	xxx	x	x.x	x.xx
				xxxxxxx	x.xx	xxx	x	x.x	x.xx
	xxxxxx	xxxxxxxxxx	xxxxx	xxxxxxx	x.xx	xxx	x	x.x	x.xx
				xxxxxxx	x.xx	xxx	x	x.x	x.xx
				xxxxxxx	x.xx	xxx	x	x.x	x.xx
				xxxxxxx	x.xx	xxx	x	x.x	x.xx

Source Listing: 16.2.9.1; Produced: yyyy-mm-ddThh:mm - Page x of y
H = Above Normal Range; Lo = Below Normal Range.

Programming Note: This table will be repeated for Part 2. Similar tables will be produced for Hematology Out of Normal Range Data - Part 1 and Part 2 (Table 14.3.2.2) and Urinalysis Out of Normal Range Data (Table 14.3.2.3).

OMO-103-01
Table 14.3.2.4
Autoimmune values - Part 1
Safety Set

<Parameter (<units>>						
Visit/ Time Point	n	Mean	SD	Min	Median	Max
SCREENING	x	x.xx	x.xxx	x.x	x.xx	x.x
CYCLE 3 DAY 01	x	x.xx	x.xxx	x.x	x.xx	x.x
CYCLE 4 DAY 01	x	x.xx	x.xxx	x.x	x.xx	x.x
...						

Source Listing: Listing 16.2.9.5; Produced: yyyy-mm-ddThh:mm - Page x of y

Programming Note: This table will be repeated for Part 2.

OMO-103-01
Table 14.3.2.5
Frequency of Autoimmune values - Part 1
Safety Set

<Parameter (<units>>		COHORT 1 (Dose xx mg/ml) (N=x)	Overall (N=x)
SCREENING	N	x (x.x)		x (x.x)
	Positive	x (x.x)		x (x.x)
	Negative	x (x.x)		x (x.x)
CYCLE 3 DAY 01	N	x (x.x)		x (x.x)
	Positive	x (x.x)		x (x.x)
	Negative	x (x.x)		x (x.x)
CYCLE 4 DAY 01	N	x (x.x)		x (x.x)
	Positive	x (x.x)		x (x.x)
	Negative	x (x.x)		x (x.x)

Source Listing: 16.2.9.5; Produced: yyyy-mm-ddThh:mm - Page x of y

Programming note: A similar table will be presented for Part 2

OMO-103-01
Table 14.3.3.1
Summary of 12-Lead ECG Data - Part 1
Safety Set

Visit/ Time Point		COHORT 1 (Dose xx mg/ml) (N=x)	Overall (N=x)
SCREENING	N	x (x.x)		x (x.x)
	Normal	x (x.x)		x (x.x)
	Abnormal NCS	x (x.x)		x (x.x)
	Abnormal CS	x (x.x)		x (x.x)
TREATMENT PERIOD	N	x (x.x)		x (x.x)
	Normal	x (x.x)		x (x.x)
	Abnormal NCS	x (x.x)		x (x.x)
	Abnormal CS	x (x.x)		x (x.x)
FOLLOW-UP PERIOD	N	x (x.x)		x (x.x)
	Normal	x (x.x)		x (x.x)
	Abnormal NCS	x (x.x)		x (x.x)
	Abnormal CS	x (x.x)		x (x.x)

Source Listing: 16.2.12.1; Produced: yyyy-mm-ddThh:mm - Page x of y

Programming note: A similar table will be presented for Part 2

OMO-103-01
Table 14.3.4.1
Statistical summaries of ECOG status by visit - Part 1
Safety Set

Visit/ Time Point		COHORT 1 (Dose xx mg/ml) (N=x)	COHORT 2 (Dose xx mg/ml) (N=x)	Overall (N=x)
SCREENING	N	x (x.x)	x (x.x)	x (x.x)	x (x.x)
	0	x (x.x)	x (x.x)	x (x.x)	x (x.x)
	1	x (x.x)	x (x.x)	x (x.x)	x (x.x)
	2	x (x.x)	x (x.x)	x (x.x)	x (x.x)
	3				
	4				
BASELINE	N	x (x.x)	x (x.x)	x (x.x)	x (x.x)
	1	x (x.x)	x (x.x)	x (x.x)	x (x.x)
	2	x (x.x)	x (x.x)	x (x.x)	x (x.x)
	3	x (x.x)	x (x.x)	x (x.x)	x (x.x)
	4				
	5				
VISITS	N	x (x.x)	x (x.x)	x (x.x)	x (x.x)
	1	x (x.x)	x (x.x)	x (x.x)	x (x.x)
	2	x (x.x)	x (x.x)	x (x.x)	x (x.x)
	3	x (x.x)	x (x.x)	x (x.x)	x (x.x)
	4				
	5				
FOLLOW-UP PERIOD	N	x (x.x)	x (x.x)	x (x.x)	x (x.x)
	1	x (x.x)	x (x.x)	x (x.x)	x (x.x)
	2	x (x.x)	x (x.x)	x (x.x)	x (x.x)
	3	x (x.x)	x (x.x)	x (x.x)	x (x.x)
	4				
	5				

Visit/ Time Point	COHORT 1 (Dose xx mg/ml) (N=x)	COHORT 2 (Dose xx mg/ml) (N=x)	Overall (N=x)
----------------------	--------------------------------------	--------------------------------------	-------	------------------

Source Listing: 16.2.15.1; Produced: yyyy-mm-ddThh:mm - Page x of y

OMO-103-01
Table 14.3.5.1
Statistical summaries of Vital Signs by visit - Part 1
Safety Set

<Parameter>			
Visit/ Time Point		COHORT 1 (Dose xx mg/ml) (N=x)	Overall (N=x)
BASELINE	n	x (x.x)	x (x.x)
	Mean	xx	xx
	SD	xx	xx
	Min	xx	xx
	Max	xx	xx
	Median	xx	xx
CYCLE 1 DAY 01	n	x (x.x)	x (x.x)
	Mean	xx	xx
	SD	xx	xx
	Min	xx	xx
	Max	xx	xx
	Median	xx	xx
Change from BASELINE to CYCLE 1 DAY 01	n	x (x.x)	x (x.x)
	Mean	xx	xx
	SD	xx	xx
	Min	xx	xx
	Max	xx	xx
	Median	xx	xx

Source Listing: 16.2.10.1; Produced: yyyy-mm-ddThh:mm - Page x of y

Programming note: Repeat pages will be required for further visits.

*Table will be repeated for each vital sign parameter.
A similar table will be presented for Part 2*

OMO-103-01
Table 14.3.6.1
Statistical summaries of Physical Examination by visit - Part 1
Safety Set

<Body system>		COHORT 1 (Dose xx mg/ml)		Overall (N=x)
Visit/ Time Point		(N=x)	
SCREENING	N	x (x.x)		x (x.x)
	Normal	x (x.x)		x (x.x)
	Abnormal NCS	x (x.x)		x (x.x)
	Abnormal CS	x (x.x)		x (x.x)
BASELINE	N	x (x.x)		x (x.x)
	Normal	x (x.x)		x (x.x)
	Abnormal NCS	x (x.x)		x (x.x)
	Abnormal CS	x (x.x)		x (x.x)
CYCLE 1 DAY 01	N	x (x.x)		x (x.x)
	Normal	x (x.x)		x (x.x)
	Abnormal NCS	x (x.x)		x (x.x)
	Abnormal CS	x (x.x)		x (x.x)

Source Listing: 16.2.11.1; Produced: yyyy-mm-ddThh:mm - Page x of y

Programming note: Repeat pages will be required for further visits.

Table will be repeated for each body system.

A similar table will be presented for Part 2

OMO-103-01
Listing 16.2.1.1
Visit Dates
Safety Set

<Study part> - <Cohort>

Subject	Visit	Treatment	Date
xxx	xxxxxxx		xxxxxx
	xxxxxxx	xxxxx	xxxxxx
	xxxxxxx	xxxxx	xxxxxx
	xxxxxxx	xxxxx	xxxxxx
	xxxxxxx		xxxxxx
xxx	xxxxxxx		xxxxxx
	xxxxxxx	xxxxx	xxxxxx
	xxxxxxx	xxxxx	xxxxxx
	xxxxxxx	xxxxx	xxxxxx
	xxxxxxx		xxxxxx
xxx	xxxxxxx		xxxxxx
	xxxxxxx	xxxxx	xxxxxx
	xxxxxxx	xxxxx	xxxxxx
	xxxxxxx	xxxxx	xxxxxx
	xxxxxxx		xxxxxx

Produced: yyyy-mm-ddThh:mm - Page x of y

Programming Note: Date may be split into Start Date and End Date if a visit spans multiple days.

OMO-103-01
Listing 16.2.1.2
Subject Disposition - (1)
All Patients Set

<Study part> - <Cohort>

Subject	Screening Number	Screening Failure	Informed Consent			Informed Re-Consent	
			Date/Time	Version	Physician Obtaining Informed Consent	Date/Time	Version
xxx	xxxx	x	xxxxxxTxx:xx	xxxxx	xxxxx	xxxxxxTxx:xx	xxxxx
xxx	xxxx	x	xxxxxxTxx:xx	xxxxx	xxxxx	xxxxxxTxx:xx	xxxxx
xxx	xxxx	x	xxxxxxTxx:xx	xxxxx	xxxxx	xxxxxxTxx:xx	xxxxx
xxx	xxxx	x	xxxxxxTxx:xx	xxxxx	xxxxx	xxxxxxTxx:xx	xxxxx
xxx	xxxx	x	xxxxxxTxx:xx	xxxxx	xxxxx	xxxxxxTxx:xx	xxxxx
xxx	xxxx	x	xxxxxxTxx:xx	xxxxx	xxxxx	xxxxxxTxx:xx	xxxxx
xxx	xxxx	x	xxxxxxTxx:xx	xxxxx	xxxxx	xxxxxxTxx:xx	xxxxx
xxx	xxxx	x	xxxxxxTxx:xx	xxxxx	xxxxx	xxxxxxTxx:xx	xxxxx
xxx	xxxx	x	xxxxxxTxx:xx	xxxxx	xxxxx	xxxxxxTxx:xx	xxxxx

Produced: yyyy-mm-ddThh:mm - Page x of y

Programming Note: Study part sub-header will be blank for screening failures.

OMO-103-01
Listing 16.2.1.2
Subject Disposition - (2)
All Patients Set

<Study part> - <Cohort>

Subject	Screening Number	Enrollment		Study Completion/Termination			Number of cycles*
		Date	Study Part	Study Completed	Date of Completion/Withdrawal	Reason for Early Withdrawal	
xxx	xxxx	xxxxxx	x	x	xxxxxx		xx
xxx	xxxx	xxxxxx	x	x	xxxxxx		x
xxx	xxxx	xxxxxx	x	x	xxxxxx	xxxxxxxxxx	xxx
xxx	xxxx	xxxxxx	x	x	xxxxxx		xx
xxx	xxxx	xxxxxx	x	x	xxxxxx		x
xxx	xxxx	xxxxxx	x	x	xxxxxx		Xx
xxx	xxxx	xxxxxx	x	x	xxxxxx	xxxxxxxxxx	x
xxx	xxxx	xxxxxx	x	x	xxxxxx		
xxx	xxxx	xxxxxx	x	x	xxxxxx		

* Cycle count includes partial cycles.
Produced: yyyy-mm-ddThh:mm - Page x of y

Programming Note: Study part sub-header will be blank for screening failures.

OMO-103-01
 Listing 16.2.3.1
 Analysis Sets

<Study part> - <Cohort>

Subject	Screening Number	Population	Included (Y/N)
xxx	xxxx	All Patients	x
		Safety	x
		Full Analysis	x
		Per-Protocol	x
xxx	xxxx	x	x
.....			

Produced: yyyy-mm-ddThh:mm - Page x of y

Programming Note: Study part sub-header will be blank for screening failures.

OMO-103-01
Listing 16.2.4.1
Demographic Information
Safety Set

<Study part> - <Cohort>

Subject	Screening Number	Year of Birth	Age (Yrs)	Gender	Race	If Mixed or Other, Specify	Height (cm)	Weight (kg)
xxx	xx	xxxxx	xxx	x	xxxxxxxx		xxx	xxx
xxx	xx	xxxxx	xxx	x	xxxxxxxx		xxx	xxx
xxx	xx	xxxxx	xxx	x	xxxxxxxx		xxx	xxx
xxx	xx	xxxxx	xxx	x	xxxxxxxx	xxxxxxxxxxxx	xxx	xxx
xxx	xx	xxxxx	xxx	x	xxxxxxxx		xxx	xxx
xxx	xx	xxxxx	xxx	x	xxxxxxxx		xxx	xxx
xxx	xx	xxxxx	xxx	x	xxxxxxxx		xxx	xxx
xxx	xx	xxxxx	xxx	x	xxxxxxxx		xxx	xxx
xxx	xx	xxxxx	xxx	x	xxxxxxxx	xxxxxxxxxxxx	xxx	xxx
xxx	xx	xxxxx	xxx	x	xxxxxxxx		xxx	xxx
xxx	xx	xxxxx	xxx	x	xxxxxxxx		xxx	xxx

Produced: yyyy-mm-ddThh:mm - Page x of y

OMO-103-01
Listing 16.2.4.2
Medical History
Safety Set

<Study part> - <Cohort>

Subject	Medical History Number	System Organ Class/ Preferred Term/ Reported Term	Date of Onset	Date Resolved/ Ongoing	Medication Taken/Treatment given?	Clinically Significant
xxx	x	xxxxxxxxxx/ xxxxxxxxxx/ xxxxxxxxxx	xxxxxxx	xxxxxxx	x	x
	x	xxxxxxxxxx/ xxxxxxxxxx/ xxxxxxxxxx	xxxxxxx	xxxxxxx	x	x
	x	xxxxxxxxxx/ xxxxxxxxxx/ xxxxxxxxxx	xxxxxxx	xxxxxxx	x	x

Produced: yyyy-mm-ddThh:mm - Page x of y
MedDRA version <x.x>.

OMO-103-01
Listing 16.2.4.3
Inclusion/Exclusion Criteria Failures
Safety Set

<Study part> - <Cohort>

Subject	Visit	Inclusion/ Exclusion	Criteria Number	Result
xxx	xxxxxx	xxxxxx	xx	xxxxxx
xxx	xxxxxx	xxxxxx	xx	xxxxxx
xxx	xxxxxx	xxxxxx	xx	xxxxxx

Produced: yyyy-mm-ddThh:mm - Page x of y

Programming Note: If there are no inclusion/exclusion criteria failures, display 'All subjects complied with the inclusion/exclusion criteria'.

OMO-103-01
Listing 16.2.5.1
Summary of OMO 103-01 dosing
Safety Set

<Study part> - <Cohort>

Subject	Cohort	Theoretical Total Dose	Actual Total Dose	Theoretical Date of Sample	Actual Date of Sample
xxx	xxxxxxxx	xx	xx	xxxxxx	xxxxxx
		xx	xx	xxxxxx	xxxxxx
		xx	xx	xxxxxx	xxxxxx
		xx	xx	xxxxxx	xxxxxx
		xx	xx	xxxxxx	xxxxxx
		xx	xx	xxxxxx	xxxxxx
		xx	xx	xxxxxx	xxxxxx
		xx	xx	xxxxxx	xxxxxx
		xx	xx	xxxxxx	xxxxxx
		xx	xx	xxxxxx	xxxxxx

Produced: yyyy-mm-ddThh:mm - Page x of y

OMO-103-01
Listing 16.2.7.1
Summary of PFS
Safety Set

<Study part> - <Cohort>

Subject	Cohort	Date	PFS Value
xxx	xxxxxxxx	xx	xx
		xx	xx
		xx	xx
		xx	xx
		xx	xx
		xx	xx
		xx	xx
		xx	xx
		xx	xx
		xx	xx
		xx	xx

Produced: yyyy-mm-ddThh:mm - Page x of y

Programming Note: Listing will be repeated for 16.2.7.2 - 16.2.7.4

OMO-103-01
Listing 16.2.7.5
QoL Questionnaire
Safety Set

<Study Part> - <Cohort>				
Subject	Cohort	Visit	Question	Result
xxxxxx	xxxx	xxx	Do you have any trouble doing strenuous activities, like carrying a heavy shopping bag or a suitcase?	x
			Do you have any trouble taking a long walk?	x
			Etc	
			How would you rate your overall quality of life during the past week?	x
		Etc		
Etc				

Produced: yyyy-mm-ddThh:mm - Page x of y

OMO-103-01
Listing 16.2.8.1
Adverse Events - (1)
Safety Set

<Study Part> - <Cohort> - <Treatment phase>

Subject	Event Number	System Organ Class/ Preferred Term/ Reported Term	Onset Date /Time	End Date/ Time/Ongoing	Date Reported	Duration (dd:hh:mm)	Time Post Dose (dd:hh:mm)	Severity
xxx	x	xxxxxxxxxx/ xxxxxxxxxx/ xxxxxxxxxx	xxxxxxx Txx:xx	xxxxxxx Txx:xx	xxxxxxx	xx:xx:xx	xx:xx:xx	xxxxxxx
xxx	x	xxxxxxxxxx/ xxxxxxxxxx/ xxxxxxxxxx	xxxxxxx Txx:xx	xxxxxxx Txx:xx	xxxxxxx	xx:xx:xx	xx:xx:xx	xxxxxxx
	x	xxxxxxxxxx/ xxxxxxxxxx/ xxxxxxxxxx	xxxxxxx Txx:xx	xxxxxxx Txx:xx	xxxxxxx	xx:xx:xx	xx:xx:xx	xxxxxxx
xxx	x	xxxxxxxxxx/ xxxxxxxxxx/ xxxxxxxxxx	xxxxxxx Txx:xx	xxxxxxx Txx:xx	xxxxxxx	xx:xx:xx	xx:xx:xx	xxxxxxx

Produced: yyyy-mm-ddThh:mm - Page x of y
 Duration: (Date/Time of Resolution-Date/Time of Onset) + 1 minute.
 Time from Dose: (Date/Time of Onset-Date/Time of Start of Dose).
 SAE = Serious Adverse Event.
 MedDRA version <x.x>.

OMO-103-01
Listing 16.2.8.1
Adverse Events - (2)
Safety Set

<Study Part> - <Cohort> - <Treatment phase>

Subject	Event Number	System Organ Class/ Preferred Term/ Reported Term	Relationship to Study Drug	SAE	SAE Criteria	Action	Outcome	Comment
xxx	x	xxxxxxxxx/ xxxxxxxxx/ xxxxxxxxx	xxxxxxxxx	x	xxxxxxxxxxxxx	xxxxxx	xxxxxx	xxxxxxxxx
xxx	x	xxxxxxxxx/ xxxxxxxxx/ xxxxxxxxx	xxxxxxxxx	x	xxxxxxxxxxxxx	xxxxxx	xxxxxx	xxxxxxxxx
	x	xxxxxxxxx/ xxxxxxxxx/ xxxxxxxxx	xxxxxxxxx	x	xxxxxxxxxxxxx	xxxxxx	xxxxxx	xxxxxxxxx
xxx	x	xxxxxxxxx/ xxxxxxxxx/ xxxxxxxxx	xxxxxxxxx	x	xxxxxxxxxxxxx	xxxxxx	xxxxxx	xxxxxxxxx

Source Listing: 16.2.7.1; Produced: yyyy-mm-ddThh:mm - Page x of y
Duration: (Date/Time of Resolution-Date/Time of Onset) + 1 minute.
Time from Dose: (Date/Time of Onset-Date/Time of Start of Dose).
SAE = Serious Adverse Event.
MedDRA version <x.x>.

OMO-103-01
Listing 16.2.9.1
Biochemistry Data
Safety Set

<Study part> - <Cohort>

Subject	Visit	Sample Date/Time	Sample ID	Parameter	Result	Units	Flag	Normal Range		Interpretation	Repeat Req.
								Lower	Upper		
xxx	xxxxxx	xxxxxxxxT xx:xx	xxxxxxx	xxxxxxx	x.xx	xxxx	x	x.x	x.xx	xxxxxxxxxxxxxxxx	x
				xxxxxxx	x.xx	xxxx		x.x	x.xx	xxxxxxxxxxxxxxxx	
				xxxxxxx	x.xx	xxxx		x.x	x.xx	xxxxxxxxxxxxxxxx	
				xxxxxxx	x.xx	xxxx		x.x	x.xx	xxxxxxxxxxxxxxxx	
				xxxxxxx	x.xx	xxxx	x	x.x	x.xx	xxxxxxxxxxxxxxxx	
				xxxxxxx	x.xx	xxxx	x	x.x	x.xx	xxxxxxxxxxxxxxxx	
				xxxxxxx	x.xx	xxxx		x.x	x.xx	xxxxxxxxxxxxxxxx	
				xxxxxxx	x.xx	xxxx		x.x	x.xx	xxxxxxxxxxxxxxxx	
				xxxxxxx	x.xx	xxxx		x.x	x.xx	xxxxxxxxxxxxxxxx	
				xxxxxxx	x.xx	xxxx	x	x.x	x.xx	xxxxxxxxxxxxxxxx	
				xxxxxxx	x.xx	xxxx		x.x	x.xx	xxxxxxxxxxxxxxxx	

Produced: yyyy-mm-ddThh:mm - Page x of y
H = Above Normal Range; Lo = Below Normal Range.

Programming note: Similar Listings will be produced for haematology (Listing 16.2.9.2), urinalysis (Listing 16.2.9.3) and other laboratory data (Listing 16.2.9.4).

OMO-103-01
Listing 16.2.10.1
Vital Signs Data
Safety Set

<Study Part> - <Cohort>

Subject	Visit/ Time Point	Date/Time	Systolic Blood Pressure (mmHg)	Diastolic Blood Pressure (mmHg)	Pulse Rate (beats/ min)	Investigator's Interpretation
xxx	xxx	xxxxxxTxx:xx	xxx	xxx	xxx	xxxxxx
	xxx	xxxxxxTxx:xx	xxx	xxx	xxx	xxxxxx
	xxx	xxxxxxTxx:xx	xxx	xxx	xxx	xxxxxx
	xxx	xxxxxxTxx:xx	xxx	xxx	xxx	xxxxxx
	xxx	xxxxxxTxx:xx	xxx	xxx	xxx	xxxxxx
	xxx	xxxxxxTxx:xx	xxx	xxx	xxx	xxxxxx
	xxx	xxxxxxTxx:xx	xxx	xxx	xxx	xxxxxx
	xxx	xxxxxxTxx:xx	xxx	xxx	xxx	xxxxxx
	xxx	xxxxxxTxx:xx	xxx	xxx	xxx	xxxxxx
	xxx	xxxxxxTxx:xx	xxx	xxx	xxx	xxxxxx

Produced: yyyy-mm-ddThh:mm - Page x of y

OMO-103-01
Listing 16.2.11.1
Physical Examination
Safety Set

<Study Part> - <Cohort>

Subject	Visit	Performed	Date	Time
xxx	xxxxxxx	x	xxxxxx	xx:xx
	xxxxxxx	x	xxxxxx	xx:xx
	xxxxxxx	x	xxxxxx	xx:xx
	xxxxxxx	x	xxxxxx	xx:xx
xxx	xxxxxxx	x	xxxxxx	xx:xx
	xxxxxxx	x	xxxxxx	xx:xx
	xxxxxxx	x	xxxxxx	xx:xx
	xxxxxxx	x	xxxxxx	xx:xx

Produced: yyyy-mm-ddThh:mm - Page x of y

OMO-103-01
Listing 16.2.12.1
12-Lead ECG Data
Safety Set

<Study Part> - <Cohort>

Subject	Period	Treatment	Visit/ Time Point	Date/Time	Heart Rate (beats/min)	PR Interval (msec)	QRS Width (msec)	QT Interval (msec)	QTcB Interval (msec)	Investigator Comment
xxx	xxxxx	xxxxxxx	xxxxxxx	xxxxxxTxx:xx	xxx	xxx	xxx	xxx	xxx	xxxxxx
			xxxxxxx	xxxxxxTxx:xx	xxx	xxx	xxx	xxx	xxx	xxxxxx
			xxxxxxx	xxxxxxTxx:xx	xxx	xxx	xxx	xxx	xxx	xxxxxx
			xxxxxxx	xxxxxxTxx:xx	xxx	xxx	xxx	xxx	xxx	xxxxxx
			xxxxxxx	xxxxxxTxx:xx	xxx	xxx	xxx	xxx	xxx	xxxxxx
	xxxxx	xxxxxxx	xxxxxxx	xxxxxxTxx:xx	xxx	xxx	xxx	xxx	xxx	xxxxxx
			xxxxxxx	xxxxxxTxx:xx	xxx	xxx	xxx	xxx	xxx	xxxxxx
			xxxxxxx	xxxxxxTxx:xx	xxx	xxx	xxx	xxx	xxx	xxxxxx
			xxxxxxx	xxxxxxTxx:xx	xxx	xxx	xxx	xxx	xxx	xxxxxx
			xxxxxxx	xxxxxxTxx:xx	xxx	xxx	xxx	xxx	xxx	xxxxxx

Produced: yyyy-mm-ddThh:mm - Page x of y

OMO-103-01
Listing 16.2.13.1
Prior Medications
Safety Set

<Study Part> - <Cohort>

Subject	Medication Number	ATC Level 4/ Preferred Term/ Medication	Dose	Dose Unit	Frequency	Indication/ AE Number	Route	Start Date /Time	Stop Date/ Time/ Ongoing
xxx	x	xxxxxxxx/ xxxxxxxx/ xxxxxxxx	xxx	xx	xxxxxx	xxxxxxxx	xxxx	xxxxxxTxx:xx	xxxxxxTxx:xx
xxx	x	xxxxxxxx/ xxxxxxxx/ xxxxxxxx	xxx	xx	xxxxxx	xxxxxxxx	xxxx	xxxxxxTxx:xx	xxxxxxTxx:xx
xxx	x	xxxxxxxx/ xxxxxxxx/ xxxxxxxx	xxx	xx	xxxxxx	xxxxxxxx	xxxx	xxxxxxTxx:xx	xxxxxxTxx:xx

Produced: yyyy-mm-ddThh:mm - Page x of y
WHO DDE version <XXXXXX>.

Programming Note: Listing to be repeated for Concomitant Medications (Listing 16.2.13.2).

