1 INTRODUCTION

1.1 GENERAL

This statistical analysis plan (SAP) describes the statistical methods to be used during the reporting and analyses of data and should be read in conjunction with the study protocol and case report form (CRF).

This version of the plan has been developed using the current approved protocol amendment version Final v2.0 dated 18 November 2021 and annotated CRF version dated 19 July 2021. Any further changes to the protocol or CRF will be reviewed for potential impact on the SAP which will be amended if it is deemed necessary.

Draft versions of the SAP will undergo review by the Statistical Reviewer, Statistical Programmer, Project Manager, Medical Writer, Principal Investigator and the Sponsor representative. The analysis plan will be finalised and approved by the Sponsor prior to Database Lock (DBL).

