1.2 CHANGES FROM PROTOCOL

Primary endpoint for part 2 will be Progression-Free Survival (PFS) instead of Objective Response Rate (ORR). The protocol stipulates 5 dose levels will be used. It was later established that more than 5 dose levels could be used if decided by the Safety Monitoring Committee (SMC).

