4 STUDY VARIABLES AND COVARIATES

4.1 PRIMARY VARIABLES

The primary endpoints are as follows:

Part 1: Dose Escalation:

- Number of patients with a DLT;
- Number of patients with ≥ 1 related AE;
- Number of patients discontinuing study treatment due to related AEs.

The RP2D will be determined at the conclusion of Part 1.

Part 2: Dose Expansion

- Progression free survival (PFS) based on RECIST v1.1 as assessed by the Investigator.

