5 DEFINITIONS AND DERIVED VARIABLES

Product/IMP: Product/IMP is taken to mean the Myc Inhibitor OMO-103 administered intravenously.

Baseline: Unless stated otherwise, baseline is defined by subject and by variable as the last non-missing value (including repeat/unscheduled assessments) before the first use of IMP.

Protocol Deviation: a deviation related to study inclusion or exclusion criteria, conduct of the trial, subject management or subject assessment. This refers to any change, divergence, or departure from the study design or procedures defined in the protocol. Protocol deviations captured in the CRF will be reviewed on a regular basis during the study and discussed at the Data Review Meeting (DRM) before Database Lock (DBL). In addition, any deviations identified during the DRM will be discussed and included in the database as necessary. All protocol deviations within the study database will be classified as either 'Major' or 'Minor' prior to DBL, details of which will be included within the Protocol Deviations log within the CTMS and a protocol deviation listing.

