10 STATISTICAL METHODS

10.1 GENERAL PRINCIPLES

- All statistical methods will be based on the International Conference on Harmonisation (ICH) E9 document “Statistical Principles for Clinical Trials”.
- All data collected will be presented within data listings.
- Generally, data listings will be sorted by subject and by period/regimen where appropriate.
- Generally, data will be summarised by period/cohort. Baseline data will be summarised overall. The format of the summaries is defined in the shells at the end of this document.
- Repeated visits will be denoted with ‘RPT’. Unscheduled visits will be denoted with ‘UNS’.
- In summary and analysis tables of continuous variables, standard descriptive statistics (N [number within analysis set, or group, or subgroup], n [number of observations included in analysis], mean, standard deviation [SD], median, minimum and maximum) will be presented. Least squares means (LSMean) and 95% confidence intervals (CI) will be presented in the

statistical analysis outputs as appropriate. For PK summaries, geometric mean and coefficient of variation (%CV) will also be used to summarise the data.

- Unless otherwise specified, the minimum and maximum statistics will be presented in summary tables to the same number of decimal places as the original data. The mean, median, LSMeans, and CI will be presented to one more decimal place than the original data. SD will be presented to two more decimal places than the original data.
- Derived PK parameters and concentration data listings and summaries will be presented to 3 significant figures (with the exception of CV%, which will be presented to 1 decimal place). The ratio of the geometric LSMeans and its associated confidence interval will be presented to 2 decimal places.
- In summary tables of categorical variables, the number of non-missing observations by category will be presented along with percentages. Unless otherwise specified, the denominator for each percentage will be the number of non-missing observations.
- All percentages will be presented to one decimal place.
- All plots will use a linear time scale for the nominal times of the visits and will be labelled by time point.

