Programming note: A similar table will be presented for Part 2 (Dose expansion)

OMO-103-01
Table 14.1.2.1
Summary of Demographic and Baseline Information - Part 1
Safety Set

Parameter	Statistic	All Subjects (N=x)
Age (yrs)	n	x
	Mean	x.x
	SD	x.xx
	Min	x
	Median	x.x
	Max	x
Height (cm)	n	x
	Mean	x.x
	SD	x.xx
	Min	x
	Median	x.x
	Max	x
Weight (kg)	n	x
	Mean	x.xx
	SD	x.xxx
	Min	x.x
	Median	x.xx
	Max	x.x
Number of pre-treatments per patient	n	x
	Mean	x.xx
	SD	x.xxx
	Min	x.x
	Median	x.xx
	Max	x.x

Source Listing: 16.2.4.1; Produced: yyyy-mm-ddThh:mm - Page x of y

Percentages are based on the total number of subjects within the Safety Set.

Programming note: A similar table will be presented for Part 2.

[Continued overleaf...]

OMO-103-01
Table 14.1.2.1
Summary of Demographic and Baseline Information - Part 1
Safety Set

Parameter		Statistic	All Subjects (N=x)
Race:	BLACK OR AFRICAN AMERICAN	n (%)	x (x.x)
	AMERICAN INDIAN OR ALASKA NATIVE	n (%)	x (x.x)
	ASIAN	n (%)	x (x.x)
	NATIVE HAWAIIAN OR OTHER PACIFIC ISLANDER	n (%)	x (x.x)
	WHITE	n (%)	x (x.x)
	MIXED	n (%)	x (x.x)
	OTHER	n (%)	x (x.x)
Gender:	M	n (%)	x (x.x)
	F	n (%)	x (x.x)

Source Listing: 16.2.4.1; Produced: yyyy-mm-ddThh:mm - Page x of y
Percentages are based on the total number of subjects within the Safety Set.

*Programming note: A similar table will be repeated for 14.1.2.2 (FAS).
A similar table will be presented for Part 2.*

OMO-103-01
Table 14.2.1.1
Summary of Progression Free Survival (PFS) - Part 1
Safety Set

Parameter	Cohort	Statistic	
PFS	Cohort 1 (Dose 0.48 mg/kg) (N=x)	n	x
		Mean	x.x
		SD	x.xx
		Min	x
		Median	x.x
		Max	x
	Cohort 2 (Dose 1.44 mg/kg) (N=x)	n	x
		Mean	x.x
		SD	x.xx
		Min	x
		Median	x.x
		Max	x
	Cohort ...		
	Overall (N=x)	n	x
		Mean	x.x
		SD	x.xx
		Min	x
		Median	x.x
Max		x	

Source Listing: 16.2.7.1; Produced: yyyy-mm-ddThh:mm - Page x of y
Percentages are based on the total number of subjects within the Safety Set.

*Programming note: A similar table will be presented for Table 14.2.1.2 (FAS) and Table 14.2.1.3 (PPS)
All tables will be repeated for Part 2.*

OMO-103-01
Table 14.2.2.1
Summary of Efficacy parameters, DCR, ORR, TTP, TTR and DOR - Part 1
Safety Set

Parameter	Cohort	Component	Statistics	Result
DCR	Cohort 1 (Dose 0.48 mg/kg) (N=x)	DCR	Ratio (%)	x.x %
		Complete Response	N	x
		Partial Response	N	x
	Cohort 2 (Dose 1.44 mg/kg) (N=x)	DCR	Ratio (%)	x.x %
		Complete Response	N	x
		Partial Response	N	x
	Cohort 2 Escalation ...	DCR	Ratio (%)	x.x %

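### The only PFS table shell, which carries the Part 2 primary endpoint, summarises PFS as an uncensored continuous variable, and the Kaplan-Meier outputs promised in SAP 11.3 are not listed for it

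*SAP*

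**What the plan says.** **Endpoint.** SAP 1.2 records the departure from the protocol: "Primary endpoint for part 2 will be Progression-Free Survival (PFS) instead of Objective Response Rate (ORR"). SAP 4.1 gives the Part 2 primary variable as "Progression free survival (PFS) based on RECIST v1.1 as assessed by the Investigator".

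**Table.** Table 14.2.1.1 in SAP section 15, headed "Summary of Progression Free Survival (PFS) - Part 1", is the only table shell for PFS. Its rows, by dose cohort and overall, are n, mean, SD, minimum, median and maximum. The programming note extends it to the FAS and PPS and adds "All tables will be repeated for Part 2". The TTP rows in Table 14.2.2.1 are the same, and that table is reused for Part 2 with OS added.

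**Figures.** SAP 11.3 says that efficacy is analysed descriptively and promises Kaplan-Meier plots for time-to-event endpoints as a class. The figure list in section 14 has four such plots: TTP (FAS, PPS) and TTR (FAS, PPS). The figure shell applies only to these, and its time axis is in hours.

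**Listing.** Listing 16.2.7.1, the source for the PFS table, shows subject, cohort, date and PFS value. It has no event/censor column, and later efficacy listings repeat its layout.

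**Definitions.** The SAP section headed "5 DEFINITIONS AND DERIVED VARIABLES" covers product, baseline and protocol deviation only. The one censoring statement is the footnote to the TTP figure. SAP 1.1 says the plan "should be read in conjunction with the study protocol and case report form (CRF"). Only the protocol synopsis is available here.

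**The concern.** PFS is a censored outcome. A patient who leaves without progression or death contributes a time known only to be a lower bound. The disposition shell foresees such exits: loss to follow-up, subject withdrawal, sponsor termination and physician decision. The PFS shell uses the same block of statistics as age and weight, and its footnote explains percentages that the table does not contain, so it appears to be a generic layout.

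The SAP does not say how a patient without progression enters the table. A programmer could enter the censored time as if it were an event time, or leave the patient out. Neither gives a sound summary of PFS. Because the table carries the main Part 2 result, what is at stake is the reported primary estimate, its missing interval, and the reader's ability to tell from the listing which times are events.

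**Working it through.** **1. Promise against output list.** SAP 11.3 names five time-to-event endpoints: PFS, DOR, TTR, TTP and OS (Part 2 only).

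| Endpoint | Kaplan-Meier figure listed | Event and censored counts in table shell |
|---|---|---|
| PFS (Part 2 primary) | none | none |
| OS | none | none shown |
| DOR | none | none shown |
| TTP | FAS, PPS | none |
| TTR | FAS, PPS | none shown |

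Two of five have a figure, and the primary endpoint is not one of them. The table list and shells provide no other PFS summary.

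**2. What the shell would report.** The plan states no PFS median, censoring rate or precision target, so there is no figure to reproduce. From the documents: 18 patients per Part 2 group (SAP 3.1). Assumed for illustration: exponential PFS with true median 3.0 months, independent exponential censoring, and censored share c from 10% to 40%.

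Rate L = ln 2 / 3.0 = 0.231 per month, so the true mean is 1/L = 4.33 months.

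If censored times are entered as values, the table summarises min(T, C):
- mean of min(T, C) = (1 − c)/L
- median of min(T, C) = (1 − c) × true median

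| c | Raw mean (true 4.33) | Raw median (true 3.0) | Low by |
|---|---|---|---|
| 10% | 3.9 | 2.7 | 10% |
| 20% | 3.5 | 2.4 | 20% |
| 30% | 3.0 | 2.1 | 30% |
| 40% | 2.6 | 1.8 | 40% |

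Simulation at n = 18 agrees: typical raw medians are 2.69, 2.40, 2.14 and 1.81, against Kaplan-Meier medians of 2.87, 2.98, 3.02 and 2.98. If censored patients are left out instead, the events-only mean in this model is low by the same share.

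**3. When the median is not biased.** Suppose all censoring is at a fixed 6 months. Then c = exp(−6 × 0.231) = 25%. The raw mean is (1 − 0.25) × 4.33 = 3.25, which is 25% low. The raw median stays at 3.0, because all censoring falls after it. With no censoring at all, the plain and Kaplan-Meier medians essentially coincide.

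**4. When the direction reverses.** Suppose the fraction f with the shortest true times drop out and are left out. The median of the rest is −ln((1 − f)/2)/L, which is 3.46 at f = 0.1 and 3.97 at f = 0.2 (15% and 32% high). Kaplan-Meier does not cure informative dropout.

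**5. Progression seen only at scans.** The Part 2 flow chart shows the first on-treatment scan in Cycle 3, which is days 43 to 63 with 3-week cycles. Later spacing is not given, so 9 and 6 weeks were assumed. Each progression is dated at the next scan and each censored patient is entered at the last scan before dropout.
- 9-weekly: the raw mean is 5.43 months with no censoring and 4.76, 4.09, 3.44 and 2.73 at 13%, 25%, 37% and 50% censored (12%, 25%, 37% and 50% low).
- 6-weekly: 5.05 months with no censoring and 4.48, 3.88, 3.33 and 2.72 at 12%, 24%, 35% and 46% censored (11%, 23%, 34% and 46% low).

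The mean is again low by about the censored share. The raw median can only move in steps between scan dates, so a small change in c can shift it by a whole scan interval or not at all. No single figure for it should be quoted.

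**6. The missing interval.** In the same scan model, at about 25% censored, typical 95% limits for a Kaplan-Meier median with 18 patients are 2.1 to 6.2 months (9-weekly) or 1.4 to 6.9 months (6-weekly). A median printed alone hides that width.

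**The case against.** The strongest reply is that a censoring-aware PFS analysis is already intended. SAP 11.3 promises Kaplan-Meier plots for all time-to-event endpoints. Section 15 calls the shells intended layouts that may change after data review, and the Part 2 table must be re-laid out anyway because its rows are dose cohorts. The TTP figures would use PROC LIFETEST, show numbers at risk and mention censoring.

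Part of this stands. A reader might infer that the sponsor decided against Kaplan-Meier methods for PFS. The documents do not support that: the missing figures are an inconsistency between 11.3 and the output list. What does not follow is that the table is therefore sound. Permission to change a layout is not a commitment to different statistics. The default for continuous variables in SAP 10.1, "n [number of observations included in analysis], mean, standard deviation [SD], median, minimum and maximum) will be presented", is what the shell follows. The sentence beginning "Least squares means (LSMean) and 95% confidence intervals (CI) will be presented in the" applies only as appropriate, belongs to the same continuous-variable rule, and is not carried into the PFS shell. A TTP curve is also not a PFS curve, since deaths may be handled differently.

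A second reply is that the PFS start, event and censoring rules may be in the full protocol. That stands. A reader might infer that the trial has no PFS definition; the synopsis and SAP cannot show this. A definition elsewhere would still not repair the table, figure list or listing.

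A third reply is that the sizes are driven by assumptions. That also stands, and they are offered only as illustration.

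**Conclusion.** Wrong as written, and it should be fixed. The table, figure-list and listing gaps are read directly from the SAP and need no assumption. Followed as laid out, the Part 2 primary summary would ignore censoring and carry no interval.

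The size rests on assumed exponential PFS, independent random censoring and censored times entered as values. Then the raw mean is low by about the censored share (10% to 40% at 10% to 40% censored). With continuous times the raw median is low by about the same, and it is unbiased if all censoring falls after it.

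A reader might infer that the trial's decisions are compromised. They are not: SAP 3.4 calls the study exploratory without a power calculation, 11.3 makes efficacy descriptive, and the Part 2 interim rule in section 8 uses response and safety. The harm is confined to the reported primary estimate and its missing interval.

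**What to change.** - **Part 2 tables, by tumour group:** replace the PFS rows, and the TTP, OS and DOR rows, with number of events, number censored, and Kaplan-Meier median with 95% CI.
- **Figures:** add Kaplan-Meier plots for PFS, OS and DOR to the list and shells, with the axis in weeks or months.
- **Listings:** add an event/censor flag and event type to Listing 16.2.7.1 and to those that repeat its layout.
- **Part 1:** list individual times with the flag and give no interval by dose cohort. The first 2 dose levels are planned with one evaluable patient each, and PFS is not a Part 1 primary endpoint.
- **Definition:** cross-refer to the protocol for the PFS start, event and censoring rule, or state it in the SAP if the protocol lacks it.

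The cost is SAP and shell wording plus routine programming before database lock. PROC LIFETEST is already specified for the TTP and TTR figures, and no new data are needed. The downside is that groups of 18 may show wide intervals or a median that is not reached.
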